In addition, we will perform exploratory analyses for additional effect modifiers that are collected after randomization and have the theoretical potential to be affected by the study group assignment:

- Surgical incision type (open, mini-invasive with endoscopy, endoscopic converted to open)
- Choice of sedatives (etomidate, ketamine, propofol, other).
- Use of vasopressor (yes/no)
- Post-induction hypotension (yes/no)
- SBP after fluid bolus infusion (continuous variable)

Handling of Missing Data

Considering the prospective feature of RCT studies and primary endpoints are short-term outcomes, we anticipate no missing primary outcomes and very rare missing values in other variables if any. All demographics and chronic medical history will be filled on site. Intraoperative data will be monitored and documented during surgeries in the operating rooms. Postoperative follow-ups

will be tracked from the electronic health records until discharge of hospital. Other 30-day follow-up data will be obtained via phone-calls, social media software, or updated medical records from any other medical units where available by trained CRCs. Therefore, missing data will not be imputed for the primary or secondary outcome. In adjusted analyses, missing data for covariates will be imputed by multiple imputation. We will combine estimates of the treatment effect and standard errors from the 10 imputed data sets on the log odds scale using Rubin's rules.

Outliers will be subject to confirmation queries to the investigators. In case of confirmation, no modifications will be made before taken into account during analyses.

Corrections for Multiple Testing

We will conduct a single primary analysis of a single primary outcome. Additional analyses are deemed exploratory and hypothesis-generating. No correction for multiple comparisons will be performed.

Table 1 Clavien-Dindo classification

Grade	Definition
Grade I	Any deviation from the normal postoperative course without the need for pharmacological treatment, or surgical, endoscopic, and radiological interventions.

Grade	Definition
	Allowed therapeutic regimens are: drugs as antiemetics, antipyretics, analgetics, diuretics and electrolytes, and physiotherapy. This grade also includes wound infections opened at the bedside
Grade II	Requiring pharmacological treatment with drugs other than such allowed for grade I complications. Blood transfusions and total parenteral nutrition are also included
Grade III	Requiring surgical, endoscopic, or radiological intervention
Grade IIIa	Intervention not under general anesthesia
Grade IIIb	Intervention under general anesthesia
Grade IV	Life-threatening complication (including central nervous system complications) requiring IC/ICU management
Grade IVa	Single organ dysfunction (including dialysis)
Grade IVb	Multiorgan dysfunction
Grade V	Death of a patient

Figure 1 Study Flowchart

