The study includes 2020 adults (≥ 18 years old) who are planning to undergo elective non-cardiac surgery with ASA grade I-III under general anesthesia that requires tracheal intubation. The trial excludes patients for whom the intervention fluids is contraindicated or should be withhold by the judgement of the attending physician (known allergy to hydroxyethyl starch and/or multiple electrolyte injection; presence of renal failure preoperatively (defined as eGFR < 30 mL/min/1.73m 2 and/or patient receiving renal replacement therapy); abnormal coagulation function (PLT $< 100\times 10^9$ /L and/or PT $< 70\%$ and / or aPTT > 35 s); severe electrolyte disorder ($\text{Na}^+ > 160$ mmol/L and/or < 120 mmol/L); increased preoperative intracranial pressure requiring dehydration treatment). The trial also excludes patients with decompensate organ dysfunction or with systematic morbidities [cardiac dysfunction (EF $< 35\%$); liver dysfunction (defined as Child-Pugh C); morbid obesity (BMI > 37.5 kg/m 2 or > 32.5 kg/m 2 with metabolic diseases)]. Patients with anticipated length of postoperative hospital stay less than 24 hours and patients scheduled for multiple operations during this hospitalization (e. g. burn patients) are also excluded from the study.

Randomisation, Allocation, Concealment and Blinding

Permute-blocked randomisation with random block sizes stratified on study sites is used. The randomisation procedure was realised using a web-based service (Research Electronic Data Capture, RedCap, developed by Vanderbilt University).

Eligible patients will be assigned to receive either colloid or crystalloid before anaesthesia induction at 1:1 ratio. Participants, caregivers, and investigators responsible for analysing data and assessing outcomes are unaware of the group assignments. Only one investigator will be unblinded and prepare the allocated intervention fluid. The blinding is achieved by covering the intervention fluid with opaque sterilized cloth bag. The fluid infusion will be conducted and finished through an infusion pump (Zhejiang Smith Medical instrument Co., Ltd., SY-1200 Infusion Pump) prior to induction of anesthesia. The unblinded investigator will not be involved in any other aspect of the surgery, anaesthesia, data recording, outcome assessment, or data analysis.

Interventions

Patients will be administered 5 ml/kg 6% Hydroxyethyl Starch 130/0.4 Electrolyte injection or 5 ml/kg multiple electrolyte injection before anaesthesia

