induction. The infusion is required to be completed within 15 minutes. A detailed study flowchart can be found in Figure 1.

All participants will receive perioperative management in accordance to standard practices in each participant site. Mechanical ventilation is configured in the (IPPV mode, with a tidal volume 6 - 8 ml/kg and a respiratory rate f 10 - 15 breaths per minute) to maintain the end-tidal carbon dioxide (EtCO₂) level at 35 ± 5 mmHg. Any form of intravenous, inhaled, or compound anesthesia is permitted. Intraoperative monitoring encompasses vital signs such as mean arterial pressure (MAP), heart rate, peripheral capillary oxygen saturation (SpO₂), temperature (either non-invasive or invasive arterial pressure), bispectral index (BIS) value (maintained between 40 and 60 during the operation), fluid volume, bleeding, urine output, as well as the use of intraoperative vasoactive and inotropic drugs. Other routine monitoring procedures include, but are not limited to, electrocardiogram (ECG), central venous pressure (CVP), cardiac output (CO), arterial blood gases, coagulation monitoring, and frequent routine laboratory examinations.

Nonsteroidal anti-inflammatory drugs (NSAIDs) will be administered 15 to 20 minutes prior to skin incision if no contraindications are used. Either local infiltration of the incision or a nerve block can be applied depending on the surgical site. Patient-controlled intravenous analgesia (PCA) is also allowed as

required. Based on the risk stratification of postoperative nausea and vomiting (PONV), double or triple therapy for postoperative nausea resistance should be provided. Postoperative muscle relaxant antagonism will be given when necessary, and the tracheal tube will be removed once the extubation requirements are met. All other anesthesia procedures will adhere to the institutional standard practices.

Data Collection and Management

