1. Incidence of hemodynamic instability, which is defined as a mean arterial pressure (MAP) dropping below 65 mmHg or decreasing by more than 20% from the baseline within 20 minutes after the induction of anesthesia.
2. Intraoperative consumption of vasopressors.
3. Length of postoperative hospital stay, calculated as the time interval between the index surgery and the patient's discharge from the hospital.
4. Rate of ideal postoperative recovery, determined as uneventful discharge within 5 days after surgery (without major complications, classified as \geq III according to the Clavien-Dindo classification, incision infection, and readmission);
5. Proportion of patients with Clavien-Dindo classification Grade IV complications, which is defined as life-threatening complications requiring ICU management, such as single organ dysfunction (including dialysis) or multiorgan dysfunction.

Exploratory outcomes

1. Each individual component of the composite primary endpoint (by organ system and by different Clavien-Dindo classification Grades)

2. 30-day all-cause mortality;
3. Incidence of unplanned ICU admission;
4. Incidence of unplanned reoperation;
5. Incidence of in-hospital complications;
6. Barthel index for activities of daily living (ADL) at 30 days after surgery.

Safety Outcomes

1. Incidence of acute kidney injury diagnosed by KDIGO criteria;³¹
2. Massive intraoperative bleeding (hemorrhage exceeds 1000 ml);
3. Episodes of intraoperative hypotension defined as SBP < 90 mm Hg or drop \geq 30% of baseline lasted for 5 min;
4. Episodes of hypertension defined as SBP > 180 mm Hg or rise \geq 30% of baseline lasted for 5 min;
5. Arrhythmia that consisted of bradycardia (heart rate < 40 beats per minutes), tachycardia (HR > 100bpm) or new onset of arrhythmia that require anti-arrhythmic drugs;
6. Airway hyper-responsiveness defined as a airway peak pressure > 40cm H₂O).

All outcomes will be discussed and evaluated by the endpoint assessment committee and documented as appropriate. All adverse events must be recorded in CRFs and documented. The reporting of SAE follows the

institutional requirement and local regulations.

STATISTICAL ANALYSIS PLAN

Scope of the Analysis plan

This Statistical Analysis Plan (SAP) presents the statistical consideration in design and analyses for COIN trial. The final manuscript will strictly follow this SAP.

Sample Sizes

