surgical procedures canceled after randomization, patients who withdrew their consent. The as-treated population is defined by the treatment that was actually received during the trial. This takes into account any deviations from the initially assigned treatment regimen, such as crossovers to the other treatments. The Per-Protocol (PP) population consists of all patients who received the assigned treatment without significant deviations from the protocol. Specifically, the analysis will be restricted to those who completed the full-term intervention as it was initially assigned. Participants with treatment interruptions will be excluded from the PP analysis. The exclusion list will be verified by the steering committee prior to lock of the database. Analyses conducted on these dataset will be treated as supplementary analyses.

General analysis Principles

The COIN trial is designed to assess the impact of preoperative colloid infusion on the occurrence of postoperative complications in surgical patients undergoing non-cardiac surgery with general anesthesia. The estimand is the difference in the incidence of postoperative complications as defined by higher than grade I Clavien-Dindo classification at 30 days after surgery between Colloid bolus administration versus crystalloid bolus administration, in patients undergo elective non-cardiac surgery under general anesthesia. The target population is patients experienced surgery procedure. The patients have the planned surgery canceled after randomization will be excluded from the

primary analyses.

In general, categorical variables are to be compared using χ^2 test or Fisher's exact test. Continuous variables will be compared via t-test or Wilcoxon's rank-sum test. Variable normality will be assessed either via the Shapiro-Wilk test or QQ-plots and residual plots. Variable transformation such as natural logarithm or square root will be applied where necessary, or non-parametric methods (such as Wilcoxon rank sum test) shall be applied.

For the analyses of primary, secondary outcomes, and the process measures, the following information will be presented:

- 📅 The number of patients included in each analysis, by treatment arm
- 📅 A summary statistic of the outcome (such as, number (%), mean (sd), media (IQR), etc), by treatment arm
- 📅 The estimated treatment effect
- 📅 A 95% confidence interval for the estimated treatment effect
- 📅 A two-sided P value

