For all analyses, a significance level of 5% will be used. Multiple comparisons will be conducted without Type I error correction and will be interpreted as exploratory.

Data Presentation and Baseline characteristics

Baseline characteristics will be summarized using descriptive statistics for whole patients cohort and for each treatment group by mean and standard

deviation or median and interquartile range for continuous variables, and the number, frequencies, and percent for categorical variables.

Durations According to Dates

For the indexed surgery, the date of randomization or admission to the intensive care unit corresponding to the surgery date will serve as day 1.

Take, for example, the calculation of the postoperative hospital stay (in days).

The formula is: (Discharge date from hospital - Date of index surgery) + 1

Exact dates will be tracked and documented.

Analysis of the primary endpoints

The primary endpoint, incidence of postoperative complications as defined by higher than grade I Clavien-Dindo classification at 30 days after surgery will be analyzed using Chi-squared test as crude analysis. Unadjusted risk ratios with 95% confidence intervals will be estimated by two-by-two table with the use of log-Normal approximation or other approximation/numeric methods as appropriate. The effect size will be expressed as risk differences (95% confidence intervals) will be estimated using Wald's likelihood ratio approximation test or other methods appropriate, with the number needed to treat as the reciprocal of the risk difference, rounded to the nearest integer.

Secondary Analyses of the primary endpoint

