Rate of ideal postoperative recovery within 5 days of surgery will be analysed using a logistic regression model, adjusting for planned surgical procedure complexity grade, ASA grade, gender, age, baseline hemoglobin, and baseline creatinine. Similar will be conducted for as above for cases of computing complexities.

Analyses of exploratory outcomes

Each individual component of the composite primary endpoint (by organ system and by different Clavien-Dindo classification Grades)

This will be analyzed using the same approach as for the analysis of the primary outcome above. Unadjusted Chi - squared test will be used.

Thirty day all-cause mortality

The expected event rate for this endpoint is extremely low. Thus, descriptive statistics will be used. Fisher exact test will be used to compare between group difference.

Incidence of unplanned ICU admission;

This outcome will be compared either using Chi-square test or Fisher exact test as appropriate depending on rate.

Incidence of unplanned reoperation

This outcome will be compared either using Chi-square test or Fisher exact test as appropriate depending on rate.

Incidence of in-hospital complications

This outcome will be compared either using Chi-square test or Fisher exact test as appropriate depending on rate.

Barthel index for activities of daily living (ADL) at 30 days after surgery.

The ADL score will be analyzed using a linear mixed model, with a random intercept for participant centers and adjusting for planned surgical procedure complexity grade, ASA grade, age, gender, baseline hemoglobin, and baseline creatinine. For any computation complexities, variable transformations or dimension reduction methods will be used.

Clavien-Dindo Grade IV - V complications within 30 days of surgery

Clavien-Dindo Grade IV - V complications within 30 days of surgery will be analyzed using a logistic regression model, adjusting for planned surgical procedure complexity grade, ASA grade, baseline hemoglobin, and baseline creatinine.

The expected event rate for this endpoint is lower than for other outcomes, thus we reduce the number of covariates that included in the model.

Analysis of Safety outcomes

Safety outcomes will be analyzed using the same method as the analysis of primary endpoints.

Interim analyses and stopping rules

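### The only named bleeding safety outcome is intraoperative loss above 1000 ml; if few patients reach it, a modest rise in blood loss could go undetected, and comparing volume as well would be a cheap gain

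*SAP*

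**What the plan says.** - **Outcome.** The SAP's Safety Outcomes list has one bleeding item: "Massive intraoperative bleeding (hemorrhage exceeds 1000 ml". It is yes/no and confined to the operation.
- **Analysis.** Analysis of Safety outcomes: "Safety outcomes will be analyzed using the same method as the analysis of primary endpoints". Under Analysis of the primary endpoints, that endpoint "will be analyzed using Chi-squared test as crude analysis", with risk ratios, risk differences and 95% confidence intervals. General analysis Principles adds "A two-sided P value" and "For all analyses, a significance level of 5% will be used".
- **Monitoring.** Interventions lists among the intraoperative measurements "fluid volume, bleeding, urine output, as well as the use of intraoperative vasoactive and inotropic drugs".
- **Eligibility.** Study Population places "abnormal coagulation function" among the exclusions for patients in whom the study fluids are contraindicated or should be withheld.
- **Bleeding after surgery.** In Table 1, Grade II covers drug treatment beyond that allowed for Grade I, and "Blood transfusions and total parenteral nutrition are also included". Bleeding that needs an intervention would be Grade III, and life-threatening bleeding needing intensive care Grade IV. Exploratory outcomes compares the composite's components by organ system and by grade, and also unplanned reoperation and unplanned ICU admission.
- **Methods for continuous variables.** General analysis Principles already provides for log transformation and the rank-sum test.

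**The concern.** Cutting a continuous measurement at a high absolute value discards most of its information. Patients well below 1000 ml in both arms count the same whether their loss rose or not. Subgroup analyses shows that the trial includes breast and thyroid, facial and ophthalmic procedures and a minor complexity grade. If few of those patients come near 1000 ml, which is an assumption because the SAP gives no case mix, they add little to the comparison.

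No other planned analysis makes up for this. Transfusion and later bleeding can count in the composite, its components, reoperation or ICU admission, but in each they are mixed with events of other causes. The DSMB's rank-sum rule under Interim analyses and stopping rules gains no sensitivity on a yes/no variable, and it also requires agreement in direction with mortality.

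At stake is how a null result is read. An imprecise comparison of a rare event may be taken as reassurance about bleeding when a modest shift could not have been seen.

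**Working it through.** **The plan's own figure.** The SAP has no power figure for bleeding; its sample size is set on the primary endpoint. From 33% v 26%, 90% power and two-sided 5%, the standard two-proportion formula gives 890 per arm. Then 890/0.90 = 989 per arm, 1978 in total, about 2% below the stated 2020. The check below uses 1010 per arm as randomised, and 1010 × 0.90 = 909 as evaluable.

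**Inputs.** From the SAP: n per arm, two-sided 5%, the 1000 ml cut-off, the chi-squared test. Assumed, because the SAP is silent: the control rate above 1000 ml, the distribution of loss, and the size of any true increase.

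**Step 1: the cut-off, with no distribution assumed.** With p̄ = (p1 + p2)/2,

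power = Φ{ [ |p2 − p1|√n − 1.96√(2p̄(1 − p̄)) ] / √(p1(1 − p1) + p2(1 − p2)) }

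- 1% v 1.5%, n = 1010: (0.1589 − 0.3080)/0.1571 = −0.949, so power is 17%.
- 2% v 3%, n = 1010: (0.3178 − 0.4327)/0.2207 = −0.521, so power is 30%.

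Over a wider range, 1010 per arm:

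| Control rate | Power, risk ratio 1.5 | Power, risk ratio 2.0 | Risk ratio detectable with 80% power |
|---|---|---|---|
| 0.5% | 11% | 26% | 3.68 |
| 1% | 17% | 46% | 2.68 |
| 2% | 30% | 75% | 2.08 |
| 3% | 43% | 90% | 1.84 |
| 5% | 64% | 99% | 1.62 |
| 10% | 93% | >99% | 1.41 |

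**Step 2: cut-off against volume.** Take loss as lognormal with median m and log-SD s, and multiply the median by r in one arm. Then p1 = P(Z > ln(1000/m)/s) and p2 = P(Z > ln(1000/(rm))/s). The cut-off uses the formula above. Log volume uses power = Φ{ (ln r / s)√(n/2) − 1.96 }.

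For m = 100 ml, s = 1.2, r = 1.2, n = 909:

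- p1 = P(Z > 1.919) = 2.75% and p2 = P(Z > 1.767) = 3.86%.
- Cut-off: (0.3353 − 0.4956)/0.2527 = −0.634, so power is 26%.
- Log volume: (0.1823/1.2) × 21.32 − 1.96 = 1.28, so power is 90%.

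Over m = 50, 100, 200 ml and s = 1.0, 1.2, 1.4, n = 909:

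| True rise in loss | Cut-off | Log volume |
|---|---|---|
| 20% | 8-51% | 79-97% |
| 30% | 12-83% | 98% to >99% |
| 50% | 26% to >99% | >99% |

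Volume has more power in every cell for 20% and 30%. The gap is widest for small rises and low medians, and nearly closes for a 50% rise at a 200 ml median, where the cut-off has 98% or more.

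**The case against.** **This is a choice of outcome, not an error.** The definition is clear, a method is assigned, and safety outcomes are often fixed in the protocol, which is not at hand. That stands as far as it goes: nothing here is contradictory. It limits the point to a recommended improvement.

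**A real increase would very likely be missed.** A reader might infer this, but the SAP does not support it. It gives neither an event rate nor a distribution, and the result turns on the assumed effect. At a 5% control rate a doubling has 99% power; at a 200 ml median a 30% rise has 73-83%. A 20% rise on a 100 ml median is only 20 ml for the median patient, and the SAP does not say what shift would matter.

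**Bleeding risk is why abnormal coagulation is excluded.** This is a natural inference, but the SAP does not give that reason.

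**Later bleeding is lost among Grade II events.** This is too strong. It may be Grade II, III or IV, and may appear under reoperation or ICU admission. What stands is that none of these isolates bleeding.

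**The trial would report no difference in bleeding.** The planned confidence intervals would show the imprecision, and Corrections for Multiple Testing calls all analyses beyond the primary one exploratory. The risk is one of misreading, not of a planned wrong claim.

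**The volume may not be stored.** Data Collection and Management names neither blood-loss volume nor transfusion among the intraoperative items. Applying a 1000 ml cut-off makes a recorded volume likely, but a bare yes/no flag is possible. Zero or minimal losses also cannot be logged directly, so the log-volume power is a best case.

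**Conclusion.** The point holds in a conditional form. A crude chi-squared test of loss above 1000 ml is the only named bleeding comparison, and it is a weak one if the event is rare: power for a 1.5-fold risk is 30% or less at control rates up to 2%. For a modest 20% rise it has 8-51% power against 79-97% for log volume, over the assumed distributions. These figures rest on assumed rates, lognormal loss, a common multiplicative shift and 909 or 1010 patients per arm; the SAP supplies only the sample size and the test. With commoner events or larger rises the cut-off can perform well. What does not depend on the exact inputs is that dichotomising at a high threshold loses information for a modest shift, while the SAP already provides methods that avoid this. It is a worthwhile, inexpensive improvement rather than a flaw that invalidates the safety analysis.

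**What to change.** 1. Keep the 1000 ml outcome as it is.
2. Add intraoperative blood loss in ml as a safety outcome. Compare it by rank-sum test or on the log scale, and state beforehand how zero losses are handled. Ideally adjust for centre and planned surgical complexity. Report an effect estimate with 95% CI: a geometric mean ratio on the log scale, or a location shift with the rank-sum test.
3. Optionally, if the records allow it, report by arm the number of patients with transfusion or postoperative bleeding to day 30.
4. Confirm before database lock that the CRF records the volume and not only a flag.

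The cost is a few lines of SAP text and a small amount of analysis. The downside is one or two more uncorrected safety comparisons, to be labelled exploratory like the other non-primary analyses. No treatment, eligibility or stopping rule changes.

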Approximately 30%-40% of patients who underwent surgery under general anaesthesia have been reported to experience hypotension between the induction and the start of the surgical procedure [1]. This circumstance is mainly caused by relative or absolute blood volume insufficiency [2]. Such insufficiency can be directly attributed to preoperative blood fasting, vasodilation induced by some anesthetic drugs, and negative inotropic effects.

Studies have suggested that the 30-day mortality rate of patients who experience an intraoperative mean arterial pressure of less than 50 mmHg doubles compared to those with an intraoperative mean arterial pressure of no less than 80 mmHg [3]. Even transient hypotension has been shown to be associated with myocardial injury, stroke, and acute kidney injury, leading to a serious deterioration of patients' prognoses [2].

Thus, since it is almost certain that preoperative fasting and/or certain induction agents can lead to post-induction hypotension, the European Society of Anesthesiology guidelines recommend that adults consume clear fluids 2 hours before elective surgery and solid foods 6 hours before [4]. However, this recommendation is restricted due to multiple reasons, and in reality, fasting times are often extended [5]. The use of vasopressors and positive inotropes can relieve hypovolemia-induced hypotension, but it may further lead to an increased myocardial load and oxygen demand [6].

The general consensus remains that rehydration can compensate for hypovolemia at baseline just before surgery [7]. Preoperative fluid infusion has been shown to reduce post-induction hypotension by more than 50%, while also reducing the use of vasoactive drugs, improving the cardiac index (CI), and reducing the early stroke volume variation (SVV) during surgery [8].

Colloids have a 1:1 intravascular volume expansion effect, whereas crystals produce only a 20% to 25% expansion due to their extracellular distribution [9].

Despite both crystalloid and colloid fluids demonstrating stabilized hemodynamic effects during acute severe hypovolemic shock, the required dosage of colloid fluid was significantly lower than that of crystalloid [9]. The associated lower heart rate in patients using colloid fluid is also more conducive to maintaining the oxygen supply balance of the myocardium [10].

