The data safety monitoring board (DSMB) will review the outcome data, safety data and recruitment data during the trial. The DSMB will recommend that the trial to stop early if:

1. There is overwhelming external evidence to convince a broad range of clinicians that one trial arm is clearly indicated or contraindicated, and this new evidence would influence patient management.
2. It becomes evident no clear outcome will be obtained.

In addition, one prespecified interim analysis for futility will be conducted at halfway point of the trial, aka after enrollment of 1010 participant with 30-day follow-up visit for the primary endpoint. The stopping boundary for futility was designed based on O'Brien-Fleming spending function and the decisions will be made by an independent Data and Safety Monitoring Board (DSMB). The defined futility stopping conditions are either $z\text{-score} > 0.263$ or if one-sided $p\text{-value} > 0.3962$. No early efficacy stop was planned for this study as we do not intend to prematurely halt the study based on the observation of early positive results.

The DSMB will also formally evaluate the safety of the trial. The safety outcomes in each group will be reviewed by the DSMB. If the *P*-value for the difference between study groups in any of the safety outcomes is 0.05 or less using a Mann-Whitney rank-sum test and is concordant in direction with the point estimate for mortality, it is recommended that the study be stopped early for safety. Additionally, the DSMB will reserve the right to stop the trial at any point.

No adjustments to the primary analysis and the sample size will be made to account for any interim analysis performed for the DSMB. All unblinded analysis for the DSMB will be performed by an independent statistician not involved in the trial, so as to maintain blinding.

Subgroup analyses

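### The arrhythmia safety outcome pools heart rates below 40, heart rates above 100 and drug-requiring arrhythmia with no planned breakdown, so it can dilute, and in some circumstances mask, an excess of the serious components

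*SAP*

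**What the plan says.** Item 5 under Safety Outcomes in the SAP is a single outcome with three ways to qualify. It begins "Arrhythmia that consisted of bradycardia (heart rate < 40 beats per minutes" and continues "tachycardia (HR > 100bpm) or new onset of arrhythmia that require anti-arrhythmic drugs". The tachycardia part carries no duration, baseline or treatment condition, and the item states no observation window. Items 3 and 4 of the same list, intraoperative hypotension and hypertension, set a duration; the hypertension item, for example, ends "rise \geq 30% of baseline lasted for 5 min".

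On analysis, the section Analysis of Safety outcomes says only: "Safety outcomes will be analyzed using the same method as the analysis of primary endpoints". That means a chi-squared test with a risk ratio and a risk difference. Analysis by component is planned for the primary composite (Exploratory outcomes; Analyses of exploratory outcomes), but not for any safety outcome.

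The DSMB rule in Interim analyses and stopping rules recommends stopping if the P-value for "any of the safety outcomes is 0.05 or less" and the direction agrees with the point estimate for mortality. The Scope of the Analysis plan commits the final paper to follow the SAP strictly.

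**The concern.** A composite is informative when its parts are of similar weight, or when the serious part is not swamped by a common, minor one. Here a heart rate of 101, for which no minimum duration is stated, counts the same as a new arrhythmia that needs a drug. If tachycardia is much the more frequent, it supplies most of the events and most of the variance, and a real difference in the rarer components becomes hard to see. If colloid also lowers the frequency of tachycardia, the two effects pull against each other and the pooled rates may look equal.

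At stake is whether the safety table and the formal DSMB trigger can pick up an excess of bradycardia or of drug-requiring arrhythmia. The primary endpoint is not affected.

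**Working it through.** **Inputs.** From the SAP: 1010 per arm (Sample Sizes) and two-sided P-values at the 5% level (General analysis Principles). The sample size belongs to the primary endpoint and is only borrowed here. As a check on it, 33% vs 26% at 90% power needs 890 per arm; 890/0.9 = 989 per arm, or 1978 in total, about 2% below the stated 2020. The SAP gives no rate and no power for item 5, so every component rate below is an assumption.

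**Formulas.** With tachycardia rate t, bradycardia rate b and drug-requiring arrhythmia rate a, taken as independent, the pooled risk is

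P = 1 − (1 − t)(1 − b)(1 − a).

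Power to find an adverse difference d is Φ[(d − 1.96·SE0)/SE1], where SE0 is the pooled and SE1 the unpooled standard error.

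**Step 1: the component alone.** Take a = 3% (colloid) vs 1% (crystalloid). Then d = 0.020, SE0 = 0.00623 and SE1 = 0.00621. Power = Φ[(0.020 − 0.01221)/0.00621] = Φ(1.25), about 90%.

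**Step 2: pooled, tachycardia equal in both arms.** Take b = 2% in both arms. At t = 20% the pooled risks are 1 − 0.80 × 0.98 × 0.97 = 23.95% and 1 − 0.80 × 0.98 × 0.99 = 22.38%. So d = 0.0157, SE0 and SE1 are both about 0.0188, and power = Φ(−1.13), about 13%. Across the range:

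| Tachycardia, both arms | Pooled, colloid | Pooled, crystalloid | Power |
|---|---|---|---|
| 5% | 9.7% | 7.8% | 32% |
| 10% | 14.5% | 12.7% | 21% |
| 20% | 24.0% | 22.4% | 13% |
| 30% | 33.5% | 32.1% | 10% |

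No treatment effect on heart rate is needed for this loss. A second set of rates gives the same picture: arrhythmia 4% vs 2% with bradycardia 1% in both arms has 75% power alone and 32%, 21%, 13% and 10% pooled. The formula treats b and a alike, so an excess of bradycardia is diluted in the same way.

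**Step 3: tachycardia falls on colloid.** The excess 3% vs 1% is cancelled exactly when 1 − t′ = (1 − t) × 0.99/0.97. At t = 20% this gives t′ = 18.35%, a relative fall of 8%. The cancelling fall is 39% at t = 5%, 19% at 10% and 5% at 30%. For example, tachycardia 17% vs 20% with b = 2% in both arms gives pooled risks of 21.1% vs 22.4%. The result then favours colloid, and the chance of a significant adverse finding is about 0.4%.

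**Step 4: cases where masking fails.** With tachycardia rare (4.25% vs 5%, the same 15% relative fall), the pooled risks are 9.0% vs 7.8%, still adverse to colloid, though power is only about 15%. With tachycardia 17% vs 20% and bradycardia rising to 4% vs 2%, they are 22.7% vs 22.4%, no longer in favour of colloid.

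**The case against.** A reader might infer that the pooled outcome will hide a true excess because the SAP itself expects colloid to lower heart rate. The documents do not support that. The Background does say "The associated lower heart rate in patients using colloid fluid is also more conducive", but the sentence before it concerns fluids "demonstrating stabilized hemodynamic effects during acute severe hypovolemic shock", not a 5 ml/kg bolus before elective surgery. It says nothing about rates above 100 or below 40. With no component rates in the SAP, masking is a possibility that depends on how common tachycardia is and how far it falls. A rise in bradycardia would push the pooled rate the other way.

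A reader might also infer that neither the final results nor the DSMB could see the harm. That goes too far as well. Anti-arrhythmic drugs are not among those allowed for grade I in Table 1, so a postoperative arrhythmia treated with one is at least grade II. It enters the primary composite, which is analysed by organ system and by grade. All adverse events are recorded, and the DSMB reviews safety data and may stop the trial at any point. Its P-value rule is in any case limited by the requirement of concordance with mortality, which the SAP expects to be extremely rare, so splitting item 5 would not by itself make that rule sensitive.

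Finally, that a single reading, or a rate already above 100 on arrival, counts as an event is a reading of a definition that is silent on window and baseline. The protocol or CRF may settle it, and an endpoint committee evaluates all outcomes.

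These points limit the claim but do not remove it. Recording events is not a planned comparison, intraoperative arrhythmia need not appear in a composite of postoperative complications, and the dilution in Step 2 needs no effect on heart rate.

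**Conclusion.** The concern stands as one of dilution, with masking possible but not shown. As written, the SAP compares one pooled arrhythmia outcome, with no duration for tachycardia and no breakdown, and feeds that outcome to the DSMB trigger. Under assumed rates and independent components, a threefold excess of drug-requiring arrhythmia (3% vs 1%, 1010 per arm) goes from about 90% power alone to between 10% and 32% pooled, for equal tachycardia of 30% down to 5%. Full cancellation needs a relative fall in tachycardia of about 5% to 8% if tachycardia is common (30% to 20%), but 39% if it is rare (5%).

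The exposure is mainly to intraoperative events. This is a weakness in one of six safety outcomes that is worth correcting.

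**What to change.** Keep the pooled item if wished, but state in the SAP that bradycardia, tachycardia and new-onset arrhythmia requiring anti-arrhythmic drugs are each reported and compared by arm, in the final safety analysis and in the DSMB reports. Make both bradycardia and drug-requiring arrhythmia visible to the DSMB rule; limiting the rule to the latter would drop bradycardia from it. State the observation window for item 5, and align the tachycardia definition with the 5-minute duration of items 3 and 4 where the recorded data allow.

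The cost is SAP wording, a few table rows and a few more uncorrected safety comparisons, which the SAP already treats as exploratory. Two points need the sponsor's confirmation:

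- **Anti-arrhythmic drugs.** The Interventions and Data Collection and Management sections name vasoactive, inotropic and vasopressor drugs but not anti-arrhythmics, so the CRF must be checked.
- **Duration and baseline.** The baseline list names blood pressure and oxygen saturation but not heart rate. The SAP is dated January 2025, with accrual due to end in March 2025. A duration or baseline criterion may therefore not be recoverable for patients already enrolled. Separate reporting of the components does not depend on it.

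The change should be fixed before any unblinded comparison of the safety data by the trial team.
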